13.4. Documenting and Reporting of Adverse Events and Serious Adverse Events by Investigators

13.4.1. Assessment of Adverse Events

Investigators will assess the occurrence of adverse events and serious adverse events at all subject evaluation time points during the study. All adverse events and serious adverse events whether volunteered by the subject, discovered by study personnel during questioning, detected through physical examination, clinically significant laboratory test, or other means, will be recorded in the subject's medical record and on the AEs CRF and, when applicable, on the Serious Adverse Event Report Form.

Each recorded adverse event or serious adverse event will be described by its duration (i.e., start and end dates), severity, regulatory seriousness criteria (if applicable), suspected relationship to the investigational product, and any actions taken.

13.4.2. Adverse Event Reporting Period

All AEs whether serious or non-serious, will be captured from the time signed and dated ICF is obtained until 30 days following the last dose of study drug. Serious adverse events reported after 30 days following the last dose of study drug should also be reported if considered related to study drug. Resolution information after 30 days should be provided.

Progressive disease should NOT be reported as an event term, but instead symptoms/clinical signs of disease progression may be reported. (See Section 11.1.1)

All adverse events, regardless of seriousness, severity, or presumed relationship to study drug, must be recorded using medical terminology in the source document. All records will need to capture the details of the duration and the severity of each episode, the action taken with respect to the study drug, investigator's evaluation of its relationship to the study drug, and the event outcome. Whenever possible, diagnoses should be given when signs and symptoms are due to a common etiology (e.g., cough, runny nose, sneezing, sore throat, and head congestion should be reported as "upper respiratory infection").

All deaths should be reported with the primary cause of death as the AE term, as death is typically the outcome of the event, not the event itself.

If a death occurs within 30 days after the last dose of study drug, the death must be reported as a serious adverse event.

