1.5.3.2. Cardiopulmonary arrest

Cardiopulmonary arrest and/or sudden death occurred in 4 (2%) of 208 patients treated with radiation therapy and cetuximab as compared to none of 212 patients treated with radiation

therapy alone in a study in locally advanced HNSCC. Three patients with prior history of coronary artery disease died at home, with myocardial infarction as the presumed cause of death. One of these patients had arrhythmia and one had congestive heart failure. Death occurred 27, 32, and 43 days after the last dose of cetuximab. One patient with no prior history of coronary artery disease died one day after the last dose of cetuximab. In a study in R/M HNSCC, fatal cardiac disorders and/or sudden death occurred in 7 (3%) of 219 patients treated with EU-approved cetuximab and platinum-based therapy with 5-FU as compared to 4 (2%) of 133 patients treated with chemotherapy alone. Five of these 7 patients in the chemotherapy plus cetuximab arm received concomitant cisplatin and 2 patients received concomitant carboplatin. All 4 patients in the chemotherapy-alone arm received cisplatin(ERBITUX package insert).

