1.5.3.4. Dermatologic Toxicity

Dermatologic toxicities, including acneiform rash, skin drying and fissuring, paronychia inflammation, infectious sequelae (for example, *S. aureus* sepsis, abscess formation, cellulitis, blepharitis, conjunctivitis, keratitis/ulcerative keratitis with decreased visual acuity, cheilitis), and hypertrichosis occurred in patients receiving cetuximab therapy. Acneiform rash occurred in 76–88% of 1373 patients receiving cetuximab in clinical trials. Severe acneiform rash occurred in 1–17% of patients. Acneiform rash usually developed within the first two weeks of therapy and resolved in a majority of the patients after cessation of treatment, although in nearly half, the event continued beyond 28 days (ERBITUX package insert).

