13. ECG

8.2.Treatment Phase

For this study, the following assessments will be performed on Cycle 1, Day 8 (+/- 3 days) of the second agent of each study treatment:

1. Brief update of medical history
2. Physical exam with vital signs, height, body weight, and pulse oximetry
3. Document concomitant medications
4. Collect adverse events
5. Labs: CBC with differential, CMP, magnesium
6. ECOG performance assessment

The following assessments will be performed on a monthly basis, coinciding with Day 1 of each subsequent cycle (+/- 3 days).

1. Brief update of medical history
2. Physical exam with vital signs, height, body weight, and pulse oximetry
3. Document concomitant medications
4. Collect adverse events
5. Labs: CBC with differential, CMP, magnesium
6. ECOG performance status assessment
7. Tumor tissue biopsy for specimen analysis and correlative testing and blood draw for correlative studies around Day 28 of cycle 1 only (+/- 7 days)

The following assessments will be performed on day 15 of each cycle (+/- 3 days), prior to cetuximab infusion:

1. Labs: CMP, magnesium

8.3.Follow-up Phase

Patients will be followed for 5 years from study entry, or until death, whichever occurs first. Patients removed from study for unacceptable adverse events will be followed until resolution or stabilization of the adverse event. Patients taken off study to undergo non-study treatment will be censored as progressive disease as of the date they begin non-protocol therapy. Patients refusing protocol-defined follow-up will be censored as to their status on the day of last contact.

Patients will be seen within 28 days of the last treatment dose. At this visit, the following assessments will be conducted:

1. Brief update of medical history
2. Physical exam with vital signs, height, body weight, and pulse oximetry
3. Labs: CBC with differential, basic metabolic panel, hepatic function panel
4. ECOG performance status assessment

5. Collect adverse events

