Appendix 1. Schedule of Assessments

SCHEDULE OF ASSESSMENTS

| Procedure | Screen/ Baseline (≤ 28 days, unless otherwise noted) | Treatment Cycles (4-week cycles) | | | | | | | | | | | | | | | | | | | | End of Treatment (within 28 days after last dose) | Follow-up (q2 months (± 14 days) from EOT) | |
|---------------------------------------|---|----------------------------------|---|---|----|----|-----------------------|---|----|----|-----------------------|---|----|----|-----------------------|---|----|----|--|---|----|---|---|----|
| | | Cycle 1 (± 3 days) | | | | | Cycle 2 (± 3 days) | | | | Cycle 3 (± 3 days) | | | | Cycle 4 (± 3 days) | | | | Each Additional Cycle (± 3 days) | | | | | |
| | | -7 | 1 | 8 | 15 | 22 | 1 | 8 | 15 | 22 | 1 | 8 | 15 | 22 | 1 | 8 | 15 | 22 | 1 | 8 | 15 | | | 22 |
| Informed Consent | X | | | | | | | | | | | | | | | | | | | | | | | |
| Eligibility | X | | | | | | | | | | | | | | | | | | | | | | | |
| Medical History | X | | | | | | | | | | | | | | | | | | | | | | | |
| HPV or p16 status ¹ | | | | | | | | | | | | | | | | | | | | | | | | |
| Demographics | X | | | | | | | | | | | | | | | | | | | | | | | |
| Concomitant Medications Assessment | X | | | X | | | X | | | | X | | | | X | | | | X | | | | X | |
| Adverse Event Assessment | X | | | X | | | X | | | | X | | | | X | | | | X | | | | X | |
| Physical Exam ² | X | | | X | | | X | | | | X | | | | X | | | | X | | | | X | |
| Vital Signs & Height | X | | | X | | | X | | | | X | | | | X | | | | X | | | | X | |
| ECOG | X | | | X | | | X | | | | X | | | | X | | | | X | | | | X | |
| CBC with Diff ³ | X | X | | X | | | X | | | | X | | | | X | | | | X | | | | X | |
| CMP and magnesium ⁴ | X | X | | X | x | | X | | x | | X | | x | | X | | x | | X | | x | | X | |
| PT/INR, aPTT | X | X | | | | | | | | | | | | | | | | | | | | | | |
| Pregnancy test ⁵ | Within 72 hours | | | | | | | | | | | | | | | | | | | | | | | |
| HIV | X | | | | | | | | | | | | | | | | | | | | | | | |
| HEP B & C | X | | | | | | | | | | | | | | | | | | | | | | | |
| T4 and TSH | X | | | | | | X | | | | X | | | | X | | | | X | | | | | |
| ECG | X | | | | | | | | | | | | | | | | | | | | | | | |
| Tumor tissue collection ⁶ | Within 42 days | | | | | | X ¹ 0 | | | | | | | | | | | | | | | | | |

[illegible]

Cycles are 28 days in length, with the exception of cycle 1, which is 35 days long due to start of ibrutinib 7 days prior to second drug.

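### The adverse event window runs to Day 30 after the last dose, but the last scheduled assessment may fall on any day up to Day 28, so 2 to about 30 days have no planned look

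*Combined protocol and SAP*

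**What the plan says.** Section 13.4.2 states that all adverse events, serious or not, "will be captured from the time signed and dated ICF is obtained until 30 days following the last dose of study drug". For deaths it adds: "If a death occurs within 30 days after the last dose of study drug, the death must be reported as a serious adverse event". After that point the rule becomes conditional: "Serious adverse events reported after 30 days following the last dose of study drug should also be reported if considered related to study drug". Section 10.1.1 makes every patient evaluable for toxicity over the same period, from consent to 30 days after the last dose.

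The closing visit is set in Section 8.3: "Patients will be seen within 28 days of the last treatment dose". Adverse events are collected there. Appendix 1 gives its End of Treatment column the same 28-day limit. Neither place gives an earliest day. Appendix 1 then has a follow-up column, every 2 months (± 14 days) counted from the end of treatment, and the adverse event row has no mark in it.

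Section 12.2.2 lists the overall frequency and severity of adverse events as a secondary endpoint. Section 13.4.1 asks investigators to assess adverse events at all evaluation time points and to record those that are volunteered or found by other means.

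**The concern.** The reporting window and the visit meant to observe it end on different days, and the visit always ends first. Even a visit on the last permitted day leaves the window open. Because there is no earliest day, a site may use the visit at which treatment is stopped as the End-of-Treatment visit and still comply with the protocol. Almost the whole 30-day period then has no scheduled contact.

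Two things follow. First, events that begin after the visit reach the record only if the patient or another clinician brings them to the site. Second, the length of active observation after the last dose differs between patients for reasons unrelated to toxicity. With 18 patients, one person whose event is not recorded moves an incidence by 1/18 = 5.6 percentage points. The unconditional death rule has the same weakness: it runs to Day 30, but no contact is scheduled to establish whether the patient was alive on Day 30.

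**Working it through.** Days are counted from the last dose, taken as Day 0.

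**Inputs**
- End of the window: Day 30 (Sections 13.4.2 and 10.1.1).
- Day of the last planned adverse event assessment, *v*: any day from 0 to 28 (Section 8.3 and Appendix 1).
- First follow-up contact: 2 months ± 14 days after the End-of-Treatment visit (Appendix 1). I take 2 months as 61 days, which is an assumption.

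**Step 1. Where adverse events are scheduled.** The adverse event row of Appendix 1 has 24 cells against 24 columns. Its marks fall at Screening, Cycle 1 Day 8, Day 1 of Cycles 2, 3 and 4, Day 1 of each additional cycle, and End of Treatment. The follow-up cell is empty.

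**Step 2. Uncovered part of the window.** Gap = 30 − *v*.

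| End-of-Treatment visit, *v* | Days without a planned assessment |
|---|---|
| 28 | 30 − 28 = 2 |
| 21 | 30 − 21 = 9 |
| 14 | 30 − 14 = 16 |
| 7 | 30 − 7 = 23 |
| 0 | 30 − 0 = 30 |

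The gap is never zero for any permitted *v*. The documents do not say how visits will spread over Days 0 to 28, so only the range can be given, not an average.

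**Step 3. Does the next contact close the gap?** The first follow-up contact falls at *v* + 61 ± 14.
- *v* = 0: Day 47 to Day 75.
- *v* = 28: Day 75 to Day 103.

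Even if a site did ask about adverse events there, it would be asking between 47 − 30 = 17 and 103 − 30 = 73 days after the window had closed.

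**Step 4. Context on late deaths.** Section 1.5.3.2 cites 4 of 208 patients with cardiopulmonary arrest or sudden death on radiotherapy plus cetuximab: 4/208 = 1.9%, which agrees with its stated 2%. One died one day after the last dose. For the other three: "Death occurred 27, 32, and 43 days after the last dose of cetuximab". Two of these four timed deaths (Days 32 and 43) lie beyond 30 days on the cetuximab clock. The section also cites 7 of 219 fatal cardiac or sudden deaths in recurrent or metastatic disease, without timing.

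**The case against.** The best reply is that recording is not confined to marked cells. Section 13.4.1 accepts events from any source, with start and end dates, so an event on Day 20 can be entered later with its true onset. It also calls for assessment at all evaluation time points, which might include follow-up contacts. This stands in part: an unscheduled event is not automatically a lost one. But capture by other means is passive. If follow-up contacts do count, Section 13.4.1 and the empty cell in Appendix 1 disagree, and the contact comes well after Day 30. Some rows of Appendix 1 below tumor tissue collection could not be read in the text available to me. The adverse event row is legible.

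A reader might go further and infer from Section 1.5.3.2 that half of late cetuximab deaths would fall outside mandatory reporting. The documents do not support that, for four reasons.
- Section 13.4.2 keeps serious events after Day 30 reportable when considered related. What ends at Day 30 is unconditional reporting. Deaths are in any case recorded for overall survival, with follow-up of 5 years or until death (Section 8.3).
- The clocks differ. Days 32 and 43 count from the last cetuximab dose, whereas the window counts from the last dose of study drug. Section 5.2 lets one drug continue while the other is held, so such a death could lie inside the window.
- Four cases from a radiotherapy setting in locally advanced disease give no rate for this trial, and seven further cited deaths have no timing.
- That an investigator would call such deaths unrelated is conjecture. Section 13.1.5 directs the possibly related category when the product is one of several plausible causes.

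A reader might also cite Section 1.5.3.4, where acneiform rash "in nearly half, the event continued beyond 28 days". That concerns how long an event lasts once it has begun, usually early in therapy. Section 13.4.2 already asks for resolution information after 30 days.

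**Conclusion.** The mismatch is on the face of the documents. Every patient has between 2 and about 30 days of the stated 30-day window without a planned adverse event assessment. Events in that stretch may be missed or may depend on passive reporting, and the secondary endpoint of adverse event frequency depends partly on when the End-of-Treatment visit took place.

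This rests on reading the 28-day limit as having no lower bound, as written, and on the adverse event row of Appendix 1 as printed. It does not show how many events would be lost, because the documents give neither the spread of visit days nor an event rate after the last dose. It is a modest defect that is cheap to repair. The late cardiac deaths are context for why the end of the window deserves an actual contact. Extending reporting of deaths or cardiac events from any cause beyond Day 30 would be an optional trade-off and is not part of this point.

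**What to change.** In Section 8.3 and Appendix 1, schedule the closing adverse event assessment at Day 30 (+7 days) after the last dose of whichever study drug is stopped later. Allow it by telephone when the End-of-Treatment visit was earlier. Mark it in the adverse event row of Appendix 1, and state in Section 13.4.2 that this contact closes the window, so that the three places agree.

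The cost is wording in those places and at most one extra telephone call per patient. No clinic visit is added.

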13.4.3. Pregnancy

Before study enrollment, subjects must agree to take appropriate measures to avoid pregnancy. However, should a pregnancy occur in a female study subject, consent to provide follow-up information regarding the outcome of the pregnancy and the health of the infant until 30 days old will be requested.

A female subject must immediately inform the Investigator if she becomes pregnant from the time of consent to 90 days after the last dose of study drug. A male subject must immediately inform the Investigator if his partner becomes pregnant from the time of consent to 90 days after the last dose of study drug. Any female subjects receiving study drug(s) who become pregnant must immediately discontinue study drug. The Investigator should counsel the subject, discussing any risks of continuing the pregnancy and any possible effects on the fetus.

Although pregnancy itself is not regarded as an adverse event, the outcome will need to be documented. Any pregnancy occurring in a female subject or male subject's partner from the time of first dose up until 90 days after the last dose of study drug must be reported. Any occurrence of pregnancy must be recorded on the Pregnancy Report Form Part I and sent via email or fax to Pharmacyclics Drug Safety, or designee, per SAE reporting timelines of learning of the event. All pregnancies will be followed for outcome, which is defined as elective termination of the pregnancy, miscarriage, or delivery of the fetus. Pregnancies with an outcome of live birth, the newborn infant will be followed until 30 days old by completing the Pregnancy Report Form Part II. Any congenital anomaly/birth defect noted in the infant must be reported as a serious adverse event.

13.4.4. Other Malignancies

All new malignant tumors including solid tumors, skin malignancies and hematologic malignancies will be reported for the duration of study treatment and during any protocol-specified follow-up periods including post-progression follow-up for overall survival. If observed, enter data in the corresponding eCRF.

13.4.5. Adverse Events of Special Interest (AESI)

Specific adverse events, or groups of adverse events, will be followed as part of standard safety monitoring activities by the Sponsor. These events (regardless of seriousness) should be reported on the Serious Adverse Event Report Form and sent via email or fax to Pharmacyclics Drug Safety, or Designee, within 24 hours of awareness.

13.4.5.1. Major Hemorrhage

Major hemorrhage is defined as any of the following:

- Any treatment-emergent hemorrhagic adverse events of Grade 3 or higher*.
- Any treatment-emergent serious adverse events of bleeding of any grade

- Any treatment-emergent central nervous system hemorrhage/hematoma of any grade

*All hemorrhagic events requiring transfusion of red blood cells should be reported as grade 3 or higher AE per CTCAE v4.03.

Events meeting the definition of major hemorrhage will be captured as an event of special interest according to Section 13.4.5 above.

13.4.6. Expediting Reporting Requirements for Serious Adverse Events

All serious adverse events and AESIs (initial and follow-up information) will be reported on FDA Medwatch (Form 3500A) or Suspect Adverse Event Report (CIOMS Form 1) IRB Reporting Form and sent via email ([contact]) or [contact]) to Pharmacyclics Drug Safety, or designee, within 24 hours of knowledge of the event. Pharmacyclics may request follow-up and other additional information from the Sponsor Investigator.

All serious adverse events that have not resolved by the end of the study, or that have not resolved upon discontinuation of the subject's participation in the study, must be followed until any of the following occurs:

- The event resolves
- The event stabilizes
- The event returns to baseline, if a baseline value/status is available
- The event can be attributed to agents other than the study drug or to factors unrelated to study conduct
- It becomes unlikely that any additional information can be obtained (subject or health care practitioner refusal to provide additional information, lost to follow up after demonstration of due diligence with follow-up efforts)

Reporting to Regulatory Agencies:

Serious adverse events will be forwarded to FDA by the IND Sponsor according to 21 CFR 312.32.

It is the responsibility of the Investigator and the research team to ensure that serious adverse events are reported according to the Code of Federal Regulations, Good Clinical Practices (GCP), the protocol guidelines, the sponsor's guidelines, and Institutional Review Board policy.

14. STUDY MANAGEMENT

14.1. Conflict of Interest

Any investigator who has a conflict of interest with this study (patent ownership, royalties, or financial gain greater than the minimum allowable by their institution, etc.) must have the conflict reviewed according to UCSD conflict of interest policy.

14.2. Institutional Review Board (IRB) Approval and Consent

The IRB should approve the consent form and protocol prior to any study-related activities. It is expected that the IRB will have the proper representation and function in accordance with federally mandated regulations.

In obtaining and documenting informed consent, the investigator should comply with the applicable regulatory requirement(s), and should adhere to Good Clinical Practice (GCP) and to ethical principles that have their origin in the Declaration of Helsinki.

Before recruitment and enrollment onto this study, the patient will be given a full explanation of the study and will be given the opportunity to review the consent form. Each consent form must include all the relevant elements currently required by the FDA Regulations and local or state regulations. Once this essential information has been provided to the patient and the investigator is assured that the patient understands the implications of participating in the study, the patient will be asked to give consent to participate in the study by signing an IRB-approved consent form.

Prior to a patient's participation in the trial, the written informed consent form should be signed and personally dated by the patient and by the person who conducted the informed consent discussion.

14.3. Required Documentation For Multi-site Studies

Before the study can be initiated at any site, the following documentation must be provided to the UCSD Moores Cancer Center Clinical Trials Office:

- A copy of the official IRB approval letter for the protocol and informed consent.
- A copy of the IRB-approved consent form
- CVs and medical licensure for the principal investigator and any associate investigators who will be involved in the study.
- Form FDA 1572 appropriately filled out and signed with appropriate documentation. (NOTE: this is required if UCSD holds the IND. Otherwise, the affiliate Investigator's signature on the protocol is sufficient to ensure compliance)
- CAP and CLIA Laboratory certification numbers and institution lab normal values.
- Executed clinical research contract.

14.4. Patient Registration

All patients must be registered with the UCSD Moores Cancer Center Clinical Trials Office before enrollment to the study. Prior to registration, eligibility criteria must be confirmed with the UCSD Study Coordinator. To register a patient, call (858)-xxx-xxx Monday through Friday,

8:00am-4:30pm Pacific Time. Study sites other than UCSD must fax informed consent documentation, completed eligibility checklist, and all source documentation for eligibility confirmation to the UCSD Clinical Trials Office ([contact]).

Patients will be given a unique sequential study number at the time of enrollment. UCSD will fax the outside study site for confirmation of patient registration, the patient's study number, and ability to start study treatment.

